Initial version dated: 08-20-2010

Study protocol for the Cytarabine (Ara-C) in Children With Acute Promyelocytic Leukemia (APL) (NCT01191541)

Principal Investigator

[name] MD

¹Department of Pediatrics, State Key Laboratory of Experimental Hematology and Division of Pediatric Blood Diseases Center, Institute of Hematology and Blood Diseases Hospital, Chinese Academy of Medical Sciences and Peking Union Medical College, Tianjin, China.

Eligibility criteria

Eligible patients were those who were less than 14 years old, were newly diagnosed with APL, and had not previously received chemotherapy. A molecular diagnosis was not required for enrollment, but a subsequent molecular confirmation, including the demonstration of PML-RARA transcripts, was required for inclusion in the analysis. Written informed consent was obtained from all patients before study entry.

Study design and treatment groups

The study was a prospective, randomized, single-centre trial. It was designed to determine whether the combination of ATRA and ATO is safe and effective in

paediatric APL and whether Ara-C can be omitted when ATO is added for 2 courses. Patients were assigned to receive ATRA plus ATO for induction followed by 1 consolidation course of idarubicin (IDA) and 1 consolidation course of a 28-day cycle of ATO. The patients were then randomly assigned using a computer-generated random allocation schedule to receive 2 courses of either daunorubicin (DNR) or DNR+Ara-C. Patients who were treated with DNR alone were included as the no-Ara-C group. Patients who were treated with DNR+Ara-C were included as the Ara-C group. The patients were subsequently treated with maintenance therapy consisting of oral ATRA, 6-mercaptopurine, and methotrexate for 1.5 years. When CR was achieved, all patients received a prophylactic intrathecal injection (cytarabine, methotrexate, and dexamethasone) for the first time. The patients with an initial white blood cell count $>10 \times 10^{9}$ /L then received intrathecal injection once every course. Patients with an indication of CNS leukaemia received intrathecal injection once

All children were monitored using reverse transcription polymerase chain reaction (RT-PCR) of bone marrow samples. After consolidation, the patients were assessed every 3 months for 1 year and then every 6 months for 1 year.

Criteria for response and end points

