Haematological complete remission (HCR) and haematologic relapse were defined as described in previous publications. Molecular remission was defined as undetectable PML/RARa fusion transcripts. Molecular relapse was defined as the detection of the fusion oncogene PML/RARa in multiple samples within 2 weeks in the same patient. Early death (ED) was considered a death that occurred within two weeks of the beginning of treatment.

Supportive measures and management of complications

Coagulopathy was treated using fresh frozen plasma or fibrinogen. Platelet transfusions were administered to maintain a platelet count above 50×10^{9} /L until any significant sign of coagulopathy was resolved. The patients were administered hydroxyurea (1-1.5 g per day), or homoharringtonine (HHT, 1-2 mg per day for 5-10 days) when their peripheral white blood cell (WBC) counts were greater than 25×10⁹/L. At the earliest manifestation of suspected differentiation syndrome, ATRA, arsenic trioxide, or both were temporarily discontinued, and intravenous dexamethasone was administered at a dose of 5-10 mg/m² until these signs and symptoms disappeared. Antibiotics and antifungal drugs were administered for fever when required.

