Statistical analysis for the Cytarabine (Ara-C) in Children With Acute

Promyelocytic Leukemia (APL) (NCT01191541)

Principal Investigator

[name] MD

¹Department of Pediatrics, State Key Laboratory of Experimental Hematology and Division of Pediatric Blood Diseases Center, Institute of Hematology and Blood Diseases Hospital, Chinese Academy of Medical Sciences and Peking Union Medical College, Tianjin, China.

Statistical analysis

The primary objective was to demonstrate the noninferiority of DNR alone compared to DNR+Ara-C in terms of the DFS rate at 2 years. Assuming a 95% rate of DFS in the two groups, a margin of -14%, 5% type 1 error, and 80% power, 31 evaluable patients per group were required to draw a noninferiority conclusion.

The characteristics of all of the included patients were summarized using cross-tabulations (for categorical variables) and quantiles (e.g., the median; for continuous variables). Nonparametric tests were used to analyse comparisons between groups (i.e., χ^2 and Fisher's exact tests for categorical variables). EFS, DFS and OS were estimated using the Kaplan -Meier method, and log-rank tests were used for comparisons. All P values were two-sided, and those with values of 0.05 or less were considered to be statistically significant. All statistical analyses were performed using SPSS software.

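### Does the two-week molecular-relapse rule clash with the visit schedule and leave the primary endpoint, 2-year DFS, unworkable?

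*Protocol*

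**What the plan says.** The SAP (Statistical analysis, first paragraph) sets the primary aim: "The primary objective was to demonstrate the noninferiority of DNR alone compared to DNR+Ara-C in terms of the DFS rate at 2 years". It assumes 95% DFS in both groups, a margin of -14 points, 5% type 1 error and 80% power, and asks for 31 evaluable children per group. On method, its second paragraph says only: "EFS, DFS and OS were estimated using the Kaplan -Meier method, and log-rank tests were used for comparisons". It gives no list of DFS events, no start date and no censoring rule.

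The Protocol (Criteria for response and end points) refers outside for the haematologic terms: "Haematological complete remission (HCR) and haematologic relapse were defined as described in previous publications". It then defines the molecular terms in consecutive sentences: "Molecular remission was defined as undetectable PML/RARa fusion transcripts", followed by "Molecular relapse was defined as the detection of the fusion oncogene PML/RARa in multiple samples within 2 weeks in the same patient". DFS is not defined there either.

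On monitoring, the Protocol (Study design and treatment groups) has two separate sentences: "All children were monitored using reverse transcription polymerase chain reaction (RT-PCR) of bone marrow samples" and "After consolidation, the patients were assessed every 3 months for 1 year and then every 6 months for 1 year". Under Eligibility criteria, "a subsequent molecular confirmation, including the demonstration of PML-RARA transcripts, was required for inclusion in the analysis", so every analysed child is transcript-positive at diagnosis.

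**The concern.** Three things look wrong when these sections are read together.

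- **Rule against schedule.** The definition needs more than one positive sample within 2 weeks, and routine visits are months apart. If only routine visits supplied samples, the definition would never be met and DFS would become haematologic relapse or death. No trigger for a repeat sample is written, and a lone positive has no stated status.
- **No earlier remission required.** Read literally, a child who never cleared the transcript and is sampled twice in 2 weeks has relapsed, although that failure may predate the randomised courses.
- **DFS is undefined.** It is not stated whether molecular relapse counts. The start date decides whether the last of the six assessments falls inside 2 years.

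The stake is the verdict on the only powered comparison, in a trial where very few failures are expected. Neither document describes blinding, so discretion over who is re-sampled could in principle differ by arm.

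**Working it through.** **1. The plan's own figure.** With failure rate 0.05 in both groups, margin 0.14, one-sided 5% and 80% power:

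n = (1.645 + 0.842)² × 2 × 0.95 × 0.05 / 0.14² = 30.0 per group, against the SAP's 31. One-sided 2.5% gives 39, so 31 fits one-sided 5%.

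Expected failures per arm: 31 × 0.05 = 1.55. One child is 1/31 = 3.2 points, and the margin is 0.14 × 31 = 4.34 children.

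**2. Rule and schedule.** Visits at 3, 6, 9, 12, 18 and 24 months after consolidation are 13.0 or 26.1 weeks apart. The spacing is not in doubt, but a contradiction follows only if the definition is confined to routine samples, and it does not say so. A requirement for several positives in a short window is the usual form of a confirmation rule: one positive prompts another sample. Such a rule never relies on two routine visits falling inside its window. Nor does the Protocol say that the 3- and 6-monthly assessments are the only occasions for PCR, and it gives no PCR timetable during treatment.

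**3. Prior remission.** Molecular remission is defined in the sentence directly before molecular relapse. Relapse ordinarily means return after remission, so few analysts would count a child who never cleared.

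**4. Dependence on the DFS definition.** If molecular relapse is not a DFS event, points 2 and 3 cannot touch the primary result. If it is, they matter only for children with an unconfirmed positive or persistent positivity. The documents give no number for either.

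**5. How much one child matters.** Exact binomial enumeration, 31 per arm, one-sided 5%, Wald / Farrington-Manning score (the SAP names no interval):

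| Situation | Wald | Score |
|---|---|---|
| Pass, 5% v 5% failures | 82.7% | 68.6% |
| One more no-Ara-C failure turns pass to fail | 23.5% | 27.3% |
| One fewer turns fail to pass | 11.6% | 18.5% |
| Pass, 19% (no Ara-C) v 5% | 7.0% | 4.9% |
| Same, one no-Ara-C failure uncounted | 16.5% | 12.0% |
| Same, one uncounted in each arm | 14.4% | 7.6% |
| Same, one uncounted in the Ara-C arm only | 5.6% | 2.6% |
| Pass, 5% v 5%, plus one never-cleared child per arm counted as failed | 65.8% | 58.5% |

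Example: 2 v 2 failures gives a Wald limit of -10.3% and passes. For 3 (no Ara-C) v 2 the limit is -3.2 - 1.645 × 6.9 = -14.6%, and it fails.

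These figures are correct, but they measure something else. The flip rates hold for any child reclassified for any reason. The rise from 7.0% to 16.5% removes a no-Ara-C failure from every simulated trial that has one, which at 19% is 1 - 0.81³¹ = 99.9% of trials. It therefore assumes an uncounted molecular relapse practically every time. The last row needs both the strained reading in step 3 and an assumed child count.

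**6. Start date.** If 18 of 24 months are counted at constant hazard, failures are 1 - 0.81^0.75 = 14.6% and 1 - 0.95^0.75 = 3.8%, a gap of 10.8 points instead of 14. That treats every failure as found at a scheduled visit. Deaths and clinically evident relapses need not wait for one, so the figure overstates the effect.

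**The case for a change.** The strongest opposing case is that this is the event definition of the only powered endpoint, and it cannot be found in either document. Convention does not tell a reader whether an unconfirmed PCR positive counts. If repeat sampling is discretionary and blinding is not described, detection could differ between arms. A few sentences would settle it.

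The factual part stands: DFS has no written events, origin or censoring rule, and no trigger for a repeat sample is written. The rest is weaker. Differential re-sampling is inferred from silence, since nothing in the documents describes sampling that depends on arm. The direction is also open: an uncounted relapse makes passing easier if it is in the no-Ara-C arm and harder if it is in the Ara-C arm.

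Nor is fuller wording clearly a gain, because each choice is debatable.

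- Excluding unconfirmed positives from DFS builds in the very scenario costed at 7.0% to 16.5%.
- Starting DFS at randomisation puts the sixth assessment beyond 24 months, which by step 6 also makes a pass easier.
- Adding failure to clear as a new event cuts power to 65.8% / 58.5% with one such child per arm. The size formula then rises from 30.0 to 46.8 per arm (failure rate 1 - 0.95 × 30/31 = 0.081).
- Writing in a repeat sample may add a marrow procedure for a child with a positive result.

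**Conclusion.** The concern does not call for a change. It identifies missing detail, but no stated rule is shown to give a wrong result. The 2-week requirement is coherent as confirmation on repeat, and the remission condition is implied by the word relapse and by the sentence before it. Both points bear on the primary analysis only through the unwritten DFS definition, which an analyst would fill with a conventional one.

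The size cannot be established, because the number of children with unconfirmed or persistent positivity is not in the documents. What can be said is that, with 1.55 expected failures per arm, one classification can decide the outcome. That follows from 31 per arm and a 14-point margin, however relapse is worded.

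This rests on two readings: that repeat samples were available outside the routine visits, and that relapse means re-detection after clearance. If the text showed that PCR was confined to the 3- and 6-month visits and that molecular relapse was a DFS event, the first point would become a real contradiction. Neither is stated.

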Statistical analysis for the Cytarabine (Ara-C) in Children With Acute

Promyelocytic Leukemia (APL) (NCT01191541)

Principal Investigator

[name] MD

¹Department of Pediatrics, State Key Laboratory of Experimental Hematology and Division of Pediatric Blood Diseases Center, Institute of Hematology and Blood Diseases Hospital, Chinese Academy of Medical Sciences and Peking Union Medical College, Tianjin, China.

Statistical analysis

The primary objective was to demonstrate the noninferiority of DNR alone compared to DNR+Ara-C in terms of the DFS rate at 2 years. Assuming a 95% rate of DFS in the two groups, a margin of -14%, 5% type 1 error, and 80% power, 31 evaluable patients per group were required to draw a noninferiority conclusion.

The characteristics of all of the included patients were summarized using cross-tabulations (for categorical variables) and quantiles (e.g., the median; for continuous variables). Nonparametric tests were used to analyse comparisons between groups (i.e., χ^2 and Fisher's exact tests for categorical variables). EFS, DFS and OS were estimated using the Kaplan -Meier method, and log-rank tests were used for comparisons. All P values were two-sided, and those with values of 0.05 or less were considered to be statistically significant. All statistical analyses were performed using SPSS software.

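### The SAP names no noninferiority rule or sidedness, and at 31 per group none of six standard rules gives both the stated 5% error and 80% power

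*SAP*

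**What the plan says.** All the relevant text is in the SAP, section Statistical analysis.

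- Objective: "The primary objective was to demonstrate the noninferiority of DNR alone compared to DNR+Ara-C in terms of the DFS rate at 2 years".
- Sample size inputs: "Assuming a 95% rate of DFS in the two groups, a margin of -14%, 5% type 1 error, and 80% power". The result is that "31 evaluable patients per group were required to draw a noninferiority conclusion".
- Analysis of DFS: Kaplan-Meier estimates, and "log-rank tests were used for comparisons".
- Sidedness: "All P values were two-sided, and those with values of 0.05 or less were considered to be statistically significant". This is a general statement; nothing ties it to the noninferiority comparison.

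Neither document gives a confidence interval for the difference in 2-year DFS, a test against -14 points, or a rule for declaring noninferiority. On follow-up, the Protocol (Study design and treatment groups) says that after consolidation "the patients were assessed every 3 months for 1 year and then every 6 months for 1 year".

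**The concern.** Error and power belong to a decision rule. With no rule named, the stated 5% and 80% cannot be attributed to anything the trial will do. The one DFS comparison that is named cannot fill the gap: a log-rank test asks whether the curves differ, and a non-significant result in 62 patients says little about a 14-point loss.

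Sidedness is also unresolved. The general two-sided 0.05 convention and the sample size point in different directions.

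At stake is the trial's main conclusion, whether Ara-C can be left out. At rates this close to 100% the common rules disagree on realistic results, so an analyst who picks the rule after seeing the data could pick the verdict. A lenient rule raises the risk of wrongly accepting omission; a stricter one leaves the trial with clearly less than the stated power.

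**Working it through.** **Inputs (SAP, Statistical analysis).** DFS 95% in each group, margin 14 points, 5% error, 80% power, n = 31 per group. The null boundary at the design point is therefore 81% on DNR alone against 95% on DNR+Ara-C.

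**1. Reproducing the 31.** The unpooled normal approximation is

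n = (z_alpha + z_beta)² × [p₁(1-p₁) + p₂(1-p₂)] / margin²

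with variance sum 2 × 0.95 × 0.05 = 0.095 and margin² = 0.0196.

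- One-sided 5%: (1.645 + 0.842)² × 0.095 / 0.0196 = 29.97, so 30. A noncentral-t version gives 79.2% power at 30 and 80.4% at 31, so exactly 31.
- Two-sided 5% (one-sided 2.5%): (1.960 + 0.842)² × 0.095 / 0.0196 = 38.04, so 39. Under this formula power at 31 is 71.5%.

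So 31 is a correct nominal answer, but only for a one-sided 5% that the SAP does not state.

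**2. Why the approximation is poor.** Expected failures per arm are 31 × 0.05 = 1.55. The lower limit can take only a few values near the margin, and the Wald variance is zero in an arm with no failures.

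**3. Exact error and power at 31 per group.** All 32 × 32 outcomes were enumerated as two independent Binomial(31, p) counts, with 2-year DFS known for everyone. Noninferiority is declared when the lower limit (or score test) for DNR alone minus DNR+Ara-C clears -14 points.

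| Rule | Error, 81% vs 95% | Power, 95% vs 95% |
|---|---|---|
| Wald, 90% interval | 6.95% | 82.7% |
| Newcombe, 90% interval | 4.95% | 68.6% |
| Farrington-Manning, one-sided 5% | 4.94% | 68.6% |
| Wald, 95% interval | 4.80% | 75.5% |
| Newcombe, 95% interval | 2.37% | 53.1% |
| Farrington-Manning, one-sided 2.5% | 1.95% | 52.4% |

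No row has error of 5% or less together with power of 80% or more. The 90% and 95% versions of Miettinen-Nurminen, Agresti-Caffo, continuity-corrected Wald and pooled Wald also fail to give both.

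**4. Error elsewhere on the margin.**

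- 90% Wald: 5.5% at control DFS 90%, 9.1% at 97%, 17.1% as control approaches 100%.
- 95% Wald: 6.1% at control 97%, maximum 6.8% at 98.6%.
- 90% Newcombe and Farrington-Manning: 4.5% at control 97%, and at most 5.6% for control DFS of 90% or more. Their overall maxima, 6.8% and 5.8%, fall at control DFS of 57% and 44%, far from the design.

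**5. Where the rules disagree (failures, DNR alone vs DNR+Ara-C).** For 2 vs 0, the difference is 29/31 - 1 = -0.0645.

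- 90% Wald: standard error √(0.9355 × 0.0645 / 31) = 0.0441, so the limit is -0.0645 - 1.645 × 0.0441 = -13.7%: noninferior.
- 95% Wald: -0.0645 - 1.960 × 0.0441 = -15.1%: not noninferior.
- 90% Newcombe: the Wilson lower limit for 29/31 is 0.8226 and the upper limit for 31/31 is 1, so the limit is -0.0645 - (0.9355 - 0.8226) = -17.7%: not noninferior.

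For 2 vs 1 the limits are -12.2%, -13.9% and -14.8%. With both arms at 95%, these two outcomes have probability 0.0536 + 0.0874 = 0.141 after rounding, which is the whole gap between 82.7% and 68.6%.

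**6. If the named test were used.** Taking a non-significant two-sided pooled two-proportion z test as a stand-in for a non-significant log-rank, the trial would find no difference about 57% of the time when the truth is 81% vs 95%.

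**7. Censoring.** The documents give no loss rate, so 5%, 10% and 20% censored before 2 years are assumptions. The simulation used exponential event times, equal independent exponential censoring, Kaplan-Meier estimates with Greenwood variance, and 200,000 replicates per scenario. The Newcombe version used an effective sample size from the Greenwood variance.

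| Rule | Power at 5%, 10%, 20% censored | Error |
|---|---|---|
| 90% Greenwood | 81%, 80%, 77% | 7.4-7.8% |
| 95% Greenwood | 71%, 69%, 68% | 4.4-4.6% |
| 90% Newcombe on Kaplan-Meier | 67%, 65%, 62% | 4.9% |

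A repeat simulation agreed within about 0.3 points.

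**The case against.** The strongest reply is that nothing was miscalculated. The 31 is what the standard formula gives; only one-sided 5% fits it, so that reading is arguably implied, and the two-sided sentence is generic. Three of the six rules run at one-sided 2.5%, where a shortfall at 31 is expected. At one-sided 5% the Wald rule meets the power and misses the error by 1.95 points. The likelihood-ratio test built for exactly these two points comes close, with 79.9% power at 4.9% error. The 17.1% figure needs control DFS near 100%, and about 86% of the outcome probability is unaffected by moving from 90% Wald to Newcombe.

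Much of this is fair. The sample size is not an arithmetic error, and the extreme error rates lie outside the design assumption. But an implied rule is still not a stated one, and the rule the formula implies is the one with the most inflated error of the six.

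Three further points stand as qualifications. The 95% Wald limit attains 4.8% against a nominal 2.5%, so it would not serve if a true one-sided 2.5% were intended. The follow-up schedule comes straight after a sentence on RT-PCR monitoring and starts after consolidation, and no DFS start point is defined, so complete 2-year follow-up is an assumption. The preference for Newcombe or Farrington-Manning is a recommendation; the essential request is that one rule be named.

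**Conclusion.** The concern holds. The SAP attaches 5% error and 80% power to a design with no noninferiority rule, and no standard rule checked delivers both at 31 per group. If the 90% Wald limit matching the sample size is used, error at the design null is about 7% and rises as control DFS exceeds 95%. If error is held near 5%, power is about 69% (Newcombe or Farrington-Manning) or 75.5% (95% Wald, with error above 5% when control DFS is 97%). At one-sided 2.5%, Newcombe and Farrington-Manning have 52-53%.

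The main figures are exact, given independent binomial outcomes, the SAP's own rates and margin, and complete 2-year follow-up. The censoring figures rest on assumed loss rates and exponential times. This should be corrected; it does not invalidate the sample size as a nominal calculation.

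**What to change.** State one primary rule with its sidedness, for example:

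> Noninferiority is concluded if the lower limit of the two-sided 90% (one-sided 5%) Newcombe interval for the difference in 2-year DFS, DNR alone minus DNR+Ara-C, lies above -14 points. Log-rank P values do not decide noninferiority.

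Newcombe or Farrington-Manning is preferred because error stays closer to nominal as control DFS rises above 95%. A 90% Wald or Greenwood interval should not decide the question. A 95% Wald interval is a real trade-off: more power at the design point, but higher error when control DFS is above 95%; if kept, disclose its attained error (4.8% at the design null, 6.1% at control 97%).

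Restate power at 31 per group for the chosen rule, say that it assumes complete 2-year follow-up, and show how it changes with censoring. If 2-year outcomes have already been seen, say so and report the limits under the other rules as well.

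**Cost.** SAP wording only, with no extra patients, but the effect on the result is not small. Stated power falls from 80% to about 69%, or 75.5% with 95% Wald. Relative to 90% Wald, Newcombe or Farrington-Manning no longer accepts 2 vs 0 or 2 vs 1 failures (14.1% probability with both arms at 95%); 95% Wald no longer accepts 2 vs 0, 3 vs 3 or 4 vs 5 (7.2%). If 80% power must be kept, the smallest sizes among those run that meet both targets are 38 per group for 95% Wald (4.7% error, 81.5% power) and 42 for 90% Newcombe or Farrington-Manning (4.7%, 80.8%). Exact power does not rise smoothly with n, so any new size should be checked directly.

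### The SAP sets a noninferiority margin of -14% for 2-year DFS but plans no analysis that uses it: the only DFS comparison named is a two-sided log-rank test

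*SAP*

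**What the plan says.** The first paragraph of the SAP's Statistical analysis section states: "The primary objective was to demonstrate the noninferiority of DNR alone compared to DNR+Ara-C in terms of the DFS rate at 2 years". The sample size follows: "Assuming a 95% rate of DFS in the two groups", with "a margin of -14%, 5% type 1 error, and 80% power, 31 evaluable patients per group were required to draw a noninferiority conclusion". It does not say whether the 5% is one-sided or two-sided.

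The second paragraph gives the whole time-to-event analysis in one sentence: the three endpoints EFS, DFS and OS get Kaplan-Meier estimates, and "log-rank tests were used for comparisons". It adds: "All P values were two-sided, and those with values of 0.05 or less were considered to be statistically significant". The other between-group tests it names, chi-square and Fisher's exact, are for categorical variables and also test equality.

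The margin is not mentioned again. The Protocol adds no statistical method. Under Study design and treatment groups it poses the question the trial must answer: "whether Ara-C can be omitted when ATO is added for 2 courses".

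**The concern.** A noninferiority claim requires rejecting the hypothesis that 2-year DFS without Ara-C is at least 14 points worse. The log-rank null is that the two DFS curves are the same throughout. A non-significant result does not exclude a 14-point loss, and a significant one does not place the 2-year difference on either side of the margin.

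The number of events makes this serious. At 95% DFS in both groups, 62 patients yield about 62 × 0.05 = 3.1 events by 2 years. A log-rank test on 3 events will almost always be non-significant, whatever that says about the margin. The SAP does not say that P above 0.05 means noninferiority. But it names no other DFS comparison on which the decision to omit Ara-C could rest, and it leaves the interval and its level open to choice after the data are seen.

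**Working it through.** **Inputs.** From the SAP: DFS 95% in both groups, margin 14 points (read as an absolute difference), 5% error, 80% power, 31 per group. Assumed here: complete 2-year follow-up, and exponential DFS in the simulations.

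**1. Which test does 31 per group correspond to?** For an unpooled (Wald) comparison of two rates with the margin,

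n = (z_alpha + z_power)² × 2 × 0.95 × 0.05 / 0.14²

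- One-sided 5%: (1.645 + 0.842)² × 0.095 / 0.0196 = 29.97, so 30 per group. Power at 31 is 81.2%.
- One-sided 2.5%: (1.960 + 0.842)² × 0.095 / 0.0196 = 38.04, so 39 per group. Power at 31 is 71.5%.

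The stated 31 is therefore close to a one-sided 5% test of the 2-year difference against the margin. That test is absent from the analysis paragraph, and its level does not match the two-sided 0.05 stated there.

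**2. A result on which the two approaches part.** Take 27/31 event-free without Ara-C and 30/31 with it.

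- Difference: 0.871 - 0.968 = -9.7 points.
- Log-rank, over all orders in which the five events can fall (no ties): P from 0.156 to 0.175, not significant.
- Wald: standard error = √(0.871 × 0.129/31 + 0.968 × 0.032/31) = 0.068; one-sided 95% lower limit = -0.097 - 1.645 × 0.068 = -20.9 points.
- Miettinen-Nurminen score: one-sided 95% lower limit -23.3 points.

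Both limits fall below -14, so noninferiority is not shown by either method, while the planned test reports no significant difference.

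**3. How often log-rank is non-significant (simulation, 31 per group).**

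| True 2-year DFS, no-Ara-C / Ara-C | Mean events | Log-rank P > 0.05 |
|---|---|---|
| 95% / 95% | 3.1 | about 97% |
| 81% / 95% (at the margin) | 7.4 | about 58% |

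At 95%/95%, the share of trials that are non-significant and also fail the margin depends on the interval: about 29% with a score-type rule, about 16% with one-sided 5% Wald.

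**4. What a stated rule would deliver (exact binomial enumeration, 31 per group).**

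| Rule | Power at 95%/95% | Type 1 error at 81%/95% |
|---|---|---|
| Score, one-sided 5% | 68.6% | 4.9% |
| Wald, one-sided 5% | 82.7% | 7.0% |
| Score, one-sided 2.5% | 52.4% | 2.0% |
| Wald, one-sided 2.5% (two-sided 95% CI) | 75.5% | 4.8% |

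These are all readings the present text allows, and power runs from 52% to 83% across them.

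**5. Arms without events.** One arm is event-free with probability 0.95^31 = 0.204, and at least one of the two with probability 1 - (1 - 0.204)² = 36.6%. Log-log Kaplan-Meier limits do not exist for such an arm, so software defaults cannot be relied on to settle the interval.

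**The case against.** The strongest reply is that the SAP implies the right analysis. It names the endpoint, the time point, the margin and the error rate, says that "31 evaluable patients per group were required to draw a noninferiority conclusion", and plans Kaplan-Meier estimates from which the 2-year difference follows. The log-rank sentence covers three endpoints together and is never called the primary test. This is fair as far as it goes: the ingredients for a margin comparison are there. But the interval method, the level and the rule are not, and the second table in the working shows that these choices matter.

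Two further points stand. The 58% is not an error rate of the plan. It would become one only if a non-significant P were read as noninferiority, in which case it would compare with about 5% for a valid margin test. And the 29% largely reflects the score-type interval, since Wald gives about 16%. The 4-versus-1 example depends on neither choice.

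It can also be said that 31 per group stands once a one-sided 95% Wald limit is written down. By the asymptotic formula it does, but the exact type 1 error of that rule at 81%/95% is 7.0%, not 5%.

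**Conclusion.** The concern holds and must be fixed. As written, the SAP contains no test or decision rule for its primary objective, and the one DFS comparison it plans cannot supply one. This follows from the text and needs no model. Nor does the 4-versus-1 example, which needs only complete 2-year follow-up. The 97% and 58% figures assume exponential DFS as well. The power and error rates assume complete 2-year data and the SAP's own 95%. The 31 per group is not itself shown to be wrong: it roughly fits a one-sided 5% Wald test, which must be reconciled with the SAP's two-sided rule.

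**What to change.** Add to the SAP: *The primary analysis is the difference in Kaplan-Meier 2-year DFS (no-Ara-C minus Ara-C) with a one-sided 95% lower limit (equivalently, a two-sided 90% confidence interval). Noninferiority is concluded only if this limit is above -14 percentage points.*

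With it:

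- State that the 5% type 1 error is one-sided, and limit the two-sided P-value sentence to the secondary comparisons. If the sponsor prefers a two-sided 95% interval, the Wald formula needs 39 per group and gives 71.5% power at 31.
- Fix the interval in advance: Miettinen-Nurminen score if every patient's 2-year status is known. If anyone is censored earlier, combine the two arms' Kaplan-Meier limits by the Newcombe (MOVER) method, using log-log limits or Wilson limits on the effective sample size, with a stated rule for an arm without events.
- Keep log-rank as secondary, and say that a non-significant P is not evidence of noninferiority.

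The cost is a few sentences, one interval calculation and a less favourable stated power: about 69% at 31 per group with the score rule and complete data. With the Wilson-based Newcombe interval it is about 66% or 63% if 10% or 20% of patients are lost before 2 years (type 1 error stays near 5%). Whether to accept that power or enrol more is a separate decision. About 41 per group, 2 × (41 - 31) = 20 more patients, would give 81.4% with the score rule and complete data.
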